3.1.6.2 Age at onset of asthma (years)

Age at onset of asthma will be calculated as the age (years) at screening minus time since asthma diagnosis (Section 3.1.6.1), rounded to the below integer.

3.1.6.3 Time since Asthma symptoms started (years)

Time from asthma first symptoms date to screening will be calculated as (date of first symptoms of asthma minus date informed consent signed plus one) divided by 365.25.

3.1.6.4 Time since last exacerbation (months)

Time since last asthma exacerbation date to screening will be calculated as (date of most recent exacerbation minus date informed consent signed plus one) divided by 365.25 and multiplied by 12.

3.1.6.5 Duration of exposure (days)

Exposure duration is calculated only for participants in the As-treated population as the total number of days on study drug. Exposure is calculated as (the study drug last injection date plus 28 days) minus study drug first injection date plus one. If any of the first or last dates are missing or partially missing, then imputed dates will not be used, and study drug exposure is set to missing.

3.1.6.6 Time from first IP administration to AE onset (days)

Time from first IP administration to AE onset will be calculated as date of AE onset minus date of first IP administration plus one.

3.1.6.7 Time from last IP administration to AE onset (days)

Time from last IP administration to AE onset will be calculated as date of AE onset minus date of last IP administration plus one.

3.1.6.8 Time from first IP administration to death (days)

Time from first IP administration to death will be calculated as date of death minus date of first IP administration plus one.

3.1.6.9 Time from last IP administration to death (days)

Time from last IP administration to death will be calculated as date of death minus date of last IP administration plus one.

3.1.7 Derivation of subgroups

Following subgroups will be explored. Any participants with a missing value for the defined subgroup will be excluded from the analysis of that subgroup. Subgroups will only be explored if there is at least 20% of the total participants in that subgroup.

- Gender (male vs female);

- Age by category (≥ 18 to < 50 vs ≥ 50 to < 65);
- Race (as entered in the eCRF);
- BMI (< 19 kg/m², ≥ 19 - < 25 kg/m², ≥ 25 - < 30 kg/m², ≥ 30 kg/m²);
- Geographical region (North America [USA], South America [Argentina], Eastern Europe [Hungary, Poland], Western Europe/Rest of the World [Germany, UK, South Africa]);
- Baseline percent predicted pre-bronchodilator FEV₁ ($< 60\%$ vs $\geq 60\%$);
- Age of asthma onset ($<$ median vs \geq median);
- Number of exacerbations in last 12 months as collected in eCRF (1 vs ≥ 2);
- Smoking status at baseline (never vs former);
- Baseline total ACQ-6 ($<$ median vs \geq median);
- Baseline total SGRQ ($<$ median vs \geq median);
- Baseline ICS total daily dose (< 500 μ g vs ≥ 500 μ g);
- Baseline blood eosinophils ($< 0.3 \times 10^9$ L vs $\geq 0.3 \times 10^9$ L);
- Background medication use (dual therapy vs triple therapy);
- Baseline FeNO (< 25 ppb vs ≥ 25 ppb);
- Baseline Total IgE (≤ 100 kU/L vs > 100 kU/L);
- Baseline mono or poly sensitised to allergen (IgE) (multiple allergens sensitisation vs single allergen sensitisation);
- T2 Corren (high vs low);
- T2 GINA (high vs low);
- SARS-CoV-2 PCR test (positive at any point vs never positive);
- SARS-CoV-2 Serology test (negative at baseline and positive at end of study vs all others);

- CCI [REDACTED]

[REDACTED]

[REDACTED]

[REDACTED]

[REDACTED]

Background medication use

Triple therapy will be defined as the combination of inhaled corticosteroids, long-acting beta-agonist and long-acting anti-muscarinic agent (ICS + LABA + LAMA). Dual therapy will be defined as ICS + LABA.

Allergen sensitisation

For the allergen specific IgE with a qualitative (positive or negative) result, a positive result and total IgE >100 kU/L will define sensitisation. For the allergen specific IgE with a quantitative result, a result equal or greater than 1.41 kU/L and total IgE > 100 kU/L will define sensitisation.

GINA T2 cut-offs

High T2 will be defined as a baseline eosinophil count of $\geq 0.15 \times 10^9$ L and/or elevated baseline FeNO (≥ 20 ppb) and/or at least one allergen sensitisation at baseline.. Other cases will correspond to Low T2.

Corren T2 cut-offs

High Th2 will be defined as a baseline total IgE level of more than 100 IU/ml (100 kU/L) and a baseline eosinophil count of 0.14×10^9 L or more; low Th2 will be defined as a baseline total IgE level of 100 IU/ml (100 kU/L) or less or baseline eosinophil count of less than 0.14×10^9 L, that is any other combination of baseline IgE and eosinophil count not included in the definition of high Th2.

CCI [Redacted]

[Redacted]

[Redacted]

[Redacted]

[Redacted]

[Redacted]

[Redacted]

[Redacted]

[Redacted]

CCI

In addition to the pre-specified sub-group analysis, further exploratory work may be carried out using sub-group identification methodology (e.g. SIDES). This analysis will be post-hoc and not included in the delivery of TFLs.

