Section 2.3.1 Risk Assessment	Updated rationale for risk of progression of heart failure	To provide information based on current data	Non-substantial

Section # and Name	Description of Change	Brief Rationale	Substantial/ Non-substantial
Section 4.1 Overall Design; Section 9.2 Sample Size Determination	Change to permit not capping randomisation of participants not included in exploratory cough sub-study solely to achieve target sample size of the sub-study	To avoid completion of exploratory sub-study delaying completion of study overall	Non-substantial
Section 5.1 Inclusion Criteria	Criterion 11: Increased the maximum permitted BMI to 40 kg/m ²	To maintain consistency with other MEDI3506 studies in context of other exclusion criteria	Substantial
Section 5.1 Inclusion Criteria	Criterion 19: Changed historic exacerbation requirement from one in 12 months to one in 24 months	To adapt to sustained fall in real world exacerbation rates secondary to the ongoing COVID-19 pandemic	Substantial
Section 5.2 Exclusion Criteria	Criterion 1: Removed the exclusion of all participants who test positive for SARS-CoV-2 at SV1. All participants who test positive at SV2 continue to be excluded.	To permit participants who test positive for SARS-CoV-2 at SV1, but negative at SV2 and who do not have symptoms meeting any other exclusion criterion to be randomised.	Substantial
Section 5.2 Exclusion Criteria	Criterion 3: Rewritten	Revised text to be clearer and consistent with other AstraZeneca studies	Substantial
Section 5.2 Exclusion Criteria; Section 1.3 Schedule of Activities, Table 1 Footnote i	Criterion 5: Removal of entire criterion which excluded participants with an NT-proBNP above the upper limit of normal.	Not considered to provide additional benefit to participant safety given other mitigations, including screening echocardiograms	Substantial

Section # and Name	Description of Change	Brief Rationale	Substantial/ Non-substantial
Section 5.2 Exclusion Criteria	Criterion 13: Removed the reference to HbA1c	To permit investigator judgement as to whether Type 2 diabetes is well controlled (and hence not exclusionary) and to maintain consistency with other MEDI3506 studies	Substantial
Section 6.5.5 COVID-19 Vaccination	Removed dose from list of information to be recorded	Information is generally not available	Non-substantial

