- 15 In countries where spermicide is available, male participants who are sexually active with a female partner of childbearing potential must agree to use a male condom with spermicide and another highly effective method of contraception during the intervention and follow-up periods from SV4 (Day 1) through to SV12 (Week 24) of the study. In countries where spermicide is not available, male participants who are sexually active with a female partner of childbearing potential must agree to use a male condom and another highly effective method of contraception during the intervention and follow-up periods from SV4 (Day 1) through to SV12 (Week 24) of the study. See [Appendix I](#) for definitions of childbearing potential and highly effective methods of contraception. Male participants should also refrain from biologically fathering a child or donating sperm during the same period.

Informed Consent

- 16 Provision of signed and dated, written informed consent (and any locally required authorisation eg, data privacy) for study participation which includes mandatory

genotyping (study objective). Note: If a participant declines to participate in the mandatory genotyping component of the study, the participant will not be included in the study.

- 17 **Optional:** provision of signed and dated written Optional Genetic Research Information informed consent prior to collection of samples for optional genetic research that supports Genomic Initiative.

Type of Participant and Disease Characteristics

- 18 Participants with documented evidence of asthma as demonstrated by either:
- Post-BD reversibility of $FEV_1 \geq 12\%$ and ≥ 200 mL (15 to 60 min after administration of 4 puffs of albuterol/salbutamol), within 12 months prior to SV1, or at SV1 or SV2. Note: if the participant cannot perform post-BD spirometry at SV1 or needs to perform a repeat assessment of post-BD spirometry, it is also acceptable to assess this criterion at SV2, **or**
 - Positive methacholine challenge test within the 12 months prior to SV1. A positive result is defined as a $PC_{20} \leq 8$ mg/mL.
- 19 Documented history of ≥ 1 asthma exacerbation in 24 months prior to SV1 (see Section 8.1.5 for definitions of acceptable documentation and asthma exacerbation).
- 20 Morning pre-BD $FEV_1 \geq 40\%$ predicted normal and > 1 L at SV1.

Criteria to be Assessed for Exploratory Cough Sub-study

Informed Consent

- 21 Provision of written dated separate ICF for the exploratory cough sub-study.

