3.2.1.4 Asthma history

The participant's asthma history will also be collected and will include questions related to the following:

- Asthma first diagnosed date;
- First appearance of asthma symptoms date;
- Most recent exacerbation date;
- Number of asthma exacerbations within previous 12 months prior to screening (including exacerbations resulted in non-emergency room treatment, emergency room treatment, hospitalization).

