6 CHANGES OF ANALYSIS FROM PROTOCOL

This SAP is based on study protocol D9181C00001 Amendment V4.0 dated 08 March 2022. Any further amendment of the study protocol which can have an impact on the SAP will lead to an amendment of this document. Changes of analysis from D9181C00001 Amendment V4.0 dated 08 March 2022 are listed here below:

Section 3 Objectives and endpoints

- Time to first CompEx event based on the period from baseline to Week 16 is a secondary endpoint for this study. However, in this SAP, a supplementary analysis including events on the period from baseline to end of follow-up (Week 24) has been added.
- An additional spirometry parameter not part of the main study endpoints (FEF25-75%) will be explored.

Section 8.1.8.3 Asthma Control Questionnaire-6

In this section it is stated that “Mean scores of ≤ 0.75 indicate well-controlled asthma, scores between 0.75 and ≤ 1.5 indicate partly controlled asthma, and scores > 1.5 indicate not well-controlled asthma”. In this SAP it is specified that “Mean scores of ≤ 0.75 indicate well-controlled asthma, scores between >0.75 and <1.5 indicate partly controlled asthma, and scores ≥ 1.5 indicate not well-controlled asthma”.

Section 9.4.2.1 Primary Endpoint

In this section it is stated that the MMRM will include “fixed effects for baseline, visit, treatment and the baseline by visit and treatment by visit interactions”. In this SAP it is mentioned that the MMRM will additionally include background medication, geographic region and baseline ICS total daily dose as fixed effects. The same variables will be added as covariates to ANCOVA, logistic regression, Cox proportional hazards and negative binomial models.

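### SAP 3.1.7: the exacerbation subgroup has no level for eligible participants with a 12-month count of 0, and both SARS-CoV-2 subgroups are defined by results obtained after randomisation

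*SAP*

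**What the plan says.** **Exacerbation factor.** SAP 3.1.7 gives two levels: "Number of exacerbations in last 12 months as collected in eCRF (1 vs ≥ 2"). The field behind it, in SAP 3.2.1.4, is the "Number of asthma exacerbations within previous 12 months prior to screening". Protocol 5.1, criterion 19, requires a "Documented history of ≥ 1 asthma exacerbation in 24 months prior to SV1". SAP section 6 says "This SAP is based on study protocol D9181C00001 Amendment V4.0 dated 08 March 2022", which is the version with the 24-month criterion. Its list of departures from the protocol does not mention this factor.

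**Rules for all factors (SAP 3.1.7).** One rule deals with absent data: "Any participants with a missing value for the defined subgroup will be excluded from the analysis of that subgroup". A second rule sets a minimum size for anything that is to be analysed: "Subgroups will only be explored if there is at least 20% of the total participants in that subgroup".

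**SARS-CoV-2 factors.** SAP 3.1.7 also lists a PCR factor (any positive result versus none) and a serology factor (negative at baseline and positive at the end of the study, versus everyone else). SAP 3.5.3.1 allows PCR testing for suspected COVID-19 throughout the intervention and follow-up periods. SAP 3.5.3.2 places the serology draws at SV4, SV10 and the early discontinuation visit.

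**Use.** SAP 4.2.4.3 fits a separate primary-endpoint MMRM for every factor in 3.1.7 and displays the results in a forest plot (Figure 14.2.1.4 in Appendix C).

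**The concern.** The exacerbation levels suit a 12-month entry rule, under which nobody should have a count of 0. The protocol's summary of changes records the switch: "Changed historic exacerbation requirement from one in 12 months to one in 24 months". The subgroup levels were not adjusted to match. Whoever programs the analysis must either drop the zeros or place them in a level by a choice that is not written down. The sponsor is unblinded at the primary data lock, so the choice should be fixed before then.

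The SARS-CoV-2 factors raise a different problem. A subgroup contrast keeps the benefit of randomisation when membership is settled before treatment starts. Here membership depends on what happens afterwards: on infection, on being tested and on how long the participant is followed. A PCR result from follow-up can even decide the subgroup for an FEV1 value already measured at Week 16. In the forest plot these rows would stand beside baseline factors and invite the same reading.

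**Working it through.** **1. Which counts are possible.**

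| Timing of the qualifying exacerbation | Meets criterion 19 | 12-month count | Level in SAP 3.1.7 |
|---|---|---|---|
| Two or more in the last 12 months | yes | 2 or more | second level |
| One in the last 12 months | yes | 1 | first level |
| None in the last 12 months, at least one in the 12 months before that | yes | 0 | none |

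The third row is observed data, so the missing-value rule does not apply to it. Participants who entered under the 12-month criterion should all have a count of at least 1, so only entrants under the 24-month criterion can fall in this row.

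**2. The 20% rule in numbers.** Planned randomisation reproduces: 216 / 0.95 = 227.4, so 228. The subgroup summaries use the ITT population (randomised and dosed), which is up to about 228. 20% of 228 is 45.6, so a level needs 46 participants.

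**3. How many zeros there might be.** The documents give neither the exacerbation rate nor the share *f* of participants who enter under the 24-month rule. Both are assumed here. With Poisson events at a constant *m* per year,

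P(0 in last 12 months, given at least 1 in 24) = e^(-m)(1 - e^(-m)) / (1 - e^(-2m)) = 1 / (1 + e^m).

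This gives 0.269 at *m* = 1 and 0.119 at *m* = 2. Multiplying by *f* and by 228:

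| *m* per year | *f* = 25% | *f* = 50% | *f* = 100% |
|---|---|---|---|
| 1 | 15 | 31 | 61 |
| 2 | 7 | 14 | 27 |

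In all six cells both planned levels exceed 46, so the contrast would run without these participants.

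The table is neither a forecast nor a bound:
- The amendment rationale cites a "sustained fall in real world exacerbation rates", so a constant rate is a simplification. Suppose the rate is 2 per year in the earlier year and 0.8 in the last. Then P(0) = e^(-0.8)(1 - e^(-2)) / (1 - e^(-2.8)) = 0.449 × 0.865 / 0.939 = 0.414. At *f* = 100% that is 94 of 228, with the upper level still at 20.4%.
- Exclusion 22 (no exacerbation within 8 weeks of SV4) empties the last few weeks before SV1. Taking 28 days, P(0) at *m* = 1 rises from 0.269 to 0.294, or 67 of 228 at *f* = 100%.
- At *m* = 0.5 the upper level among 24-month entrants is only 14.3%. If *f* is large it fails the 20% rule, and whether the whole factor or only that level is then dropped depends on how the rule is read.

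**4. Timing of the SARS-CoV-2 factors against randomisation (Day 1) and the endpoint (Week 16).**

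| Factor | Results before Day 1 | Results after Day 1 | Results after Week 16 |
|---|---|---|---|
| PCR | can count | can count | can count (follow-up to Week 24) |
| Serology | SV4 draw is part of the definition | always needed (SV10 or early discontinuation) | not scheduled beyond SV10 or early discontinuation |

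Membership in both factors therefore depends on post-randomisation results. A positive level would need 46 of 228 to be shown; the documents do not allow that number to be predicted.

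**The case against.** The best case for leaving the text alone is that little depends on it. The analyses are exploratory, and participants with a count of 0 stay in the primary analysis and the other subgroup analyses. The 12-month count is summarised by arm (Table 14.1.7.3) and listed, so zeros would be visible. Other factors also need not place everyone: single versus multiple allergen sensitisation has no level for the unsensitised. The SARS-CoV-2 labels disclose their timing, and their rows appear only if the 20% rule is met. All of this stands and limits the weight of the point. It does not supply the missing rule for zeros, and disclosing the timing does not make the contrasts randomised ones.

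Three stronger readings are tempting, and the documents do not support them.

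- *A reader might infer that the protocol says MEDI3506 changes the chance of catching SARS-CoV-2, so that membership is known to depend on treatment.* Protocol 2.3.1 lists serious infections, including those with this virus, as a potential risk. It then says the sponsor knows of no current evidence linking IL-33 suppression with contracting the virus. The factors are PCR positivity and seroconversion, not serious infection. What remains is the general objection to post-randomisation subgroups.
- *A reader might want a ceiling on the number left out.* Any ceiling depends on the assumed rate pattern, as the falling-rate case shows.
- *A reader might infer that on-study infection is otherwise unreported.* SAP 4.2.7.6 and Tables 14.3.8.6.1 and 14.3.8.6.2 already cover it.

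**Conclusion.** Both parts hold as matters of definition. The exacerbation factor omits a count that criterion 19 admits, and no SAP rule says what to do with it. The number affected is not given in the documents and may be small; the illustrative figures rest wholly on assumed rates and an assumed share of 24-month entrants. The two SARS-CoV-2 factors would yield contrasts not protected by randomisation, but only if their levels reach 20%, and no size or direction of bias is claimed. The primary test, its hierarchy and its power are untouched. The correction is worth making because it costs almost nothing and removes an unwritten choice and two rows that are easily misread.

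**What to change.** **Exacerbation factor.** Define the levels as 0-1 versus 2 or more, so that every eligible count has a place. The three-level form 0 / 1 / 2 or more can be used if each level meets the 20% rule (about 46 of 228). The cost is one line of the SAP and relabelled outputs, with no new data. Pooling 0 with 1 gives up a pure level of 1.

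**SARS-CoV-2 factors.** Remove both from the primary-endpoint subgroup MMRM and the forest plot, and rely on the infection summaries already planned in SAP 4.2.7.6 and Tables 14.3.8.6.1 and 14.3.8.6.2. If FEV1 is still wanted by infection status, show it separately, label it post-randomisation and descriptive, and use only results up to Week 16. The cost is two exploratory rows, which would have appeared only if the 20% rule was met.

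Make both changes before the primary data lock.

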3.2 Baseline assessments and other subject-specific characteristics

Demographic and subject characteristics, medical history and nicotine and alcohol use are collected pre-treatment as per study protocol's SoA.

3.2.1.1 Demographics and subject-specific characteristics

Demographic and subject characteristics include age, age group ($\geq 18 - < 50$; $\geq 50 - 65$), age group for EudraCT reporting purpose ($\geq 18 - < 65$; ≥ 65), sex, race, ethnic group, country, height (cm), weight (kg), body mass index (BMI) (kg/m^2), previous treatments containing ICS and combination of products containing ICS, asthma characteristics at baseline. Age in years will be used as provided in the IWRS (Interactive Web Response System). BMI (kg/m^2) is calculated as described in Section 3.5.2.

Height, weight and BMI are allocated to the analysis visits as per Section 3.1.4. Evaluations with missing or partially missing dates cannot be imputed to any analysis visit. Only baseline values are included in the demographic and subject characteristics.

3.2.1.2 Medical history

Medical history includes disease related and relevant medical history as collected in eCRF. Disease related and relevant medical history are coded with Medical Dictionary for Regulatory Activities (MedDRA) version 25.0 or higher.

3.2.1.3 Prior and concomitant medication

The WHO-DD March 2022 B3 Global or later is used to classify medications by WHO Anatomical Therapeutic Chemical (ATC) classification of ingredients.

The imputation method described in Section 3.1.5.2 is used in case of medication stop date partially missing. Completely missing stop date are not to be imputed. Completely missing or partially missing concomitant medication start dates are not imputed.

After the end date imputation, the medications will be classified as either prior or concomitant (but not both) according to its stop date. Prior medication is defined as any medication with a stop date prior to the first dose of IP (exclusive). Concomitant medication is defined as any medication with a stop date on or after the first dose of study drug, or any medication taken prior to study drug and that is ongoing. Medications with completely missing stop date are classified as concomitant.

Disallowed medications will include medications defined as prohibited according to CSP. They will be defined following a physician review (prior to any study delivery) of the unique combinations of ATC code classifications and generic terms captured and detailed in the Integrated Data Review Plan (IDRP).

3.2.1.4 Asthma history

The participant's asthma history will also be collected and will include questions related to the following:

- Asthma first diagnosed date;
- First appearance of asthma symptoms date;
- Most recent exacerbation date;
- Number of asthma exacerbations within previous 12 months prior to screening (including exacerbations resulted in non-emergency room treatment, emergency room treatment, hospitalization).

3.2.1.5 Substance usage

Alcoholic beverages status and consumption, and past smoking status (cigarettes, cigars, pipes, smokeless tobacco and non-tobacco nicotine products) together with the consumption of cigarettes in pack-years will be collected.

